7.4.1 Adverse Events

7.4.1.1 Adverse Event Definitions

Adverse Event

An AE is any untoward medical occurrence in a subject or clinical investigation subject administered a pharmaceutical product, regardless of causal relationship with this treatment. An AE can therefore be any unfavorable and unintended sign (including an abnormal laboratory finding), symptom, or disease temporally associated with the use of a medicinal product, whether or not considered related to the medicinal product.

For surgical or diagnostic procedures, the condition/illness leading to such a procedure is considered as the AE rather than the procedure itself.

The Investigator is required to grade the severity or toxicity of each AE.

Investigators will reference the NCI-CTCAE v4.03 (publication date: 14 June 2010), a descriptive terminology that can be used for AE reporting.

A general grading (severity/intensity; hereafter referred to as severity) scale is provided at the beginning of the above referenced document, and specific event grades are also provided.

If a particular AE's severity is not specifically graded by the guidance document, the Investigator is to use the general NCI-CTCAE definitions of Grade 1 through Grade 5 following his or her best medical judgment.

The 5 general grades are:

- Grade 1 or Mild
- Grade 2 or Moderate
- Grade 3 or Severe
- Grade 4 or Life-threatening
- Grade 5 or Death

According to Sponsor convention, any clinical AE with severity of Grade 4 or 5 must also be reported as an SAE. However, a laboratory abnormality of Grade 4, such as anemia or neutropenia, is considered serious only if the condition meets one of the serious criteria described below.

If death occurs, the primary cause of death or event leading to death should be recorded and reported as an SAE. "Fatal" will be recorded as the outcome of this specific event and death will not be recorded as separate event. Only, if no cause of death can be reported (for example, sudden death, unexplained death), the death per se might then be reported as an SAE.

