## 16.1 Adverse Events

Treatment-emergent adverse events (TEAEs) are those events with onset dates occurring during the on-treatment period or if the worsening of an event is during the on-treatment period. In this study, there are two on-treatment periods, one for Induction Phase and one for Maintenance Phase.

All analyses described will be based on TEAEs (started during the on-treatment period) if not otherwise specified. The AE listings will include all AEs (whether treatment-emergent or not). AEs outside the on-treatment period will be flagged in the listings.

- **Related Adverse Events:** adverse events with relationship to study treatment (as recorded on the AE eCRF page, Relationship with study treatment = Related) reported by the investigator and those of unknown relationship (i.e. no answer to the question “Relationship with study treatment”).
- **Serious Adverse Events (SAE):** serious adverse events (as recorded on the AE eCRF page, Serious Adverse Event = Yes).
- **Adverse Events Leading to Treatment Discontinuation:** adverse events leading to permanent discontinuation of study treatment (as recorded on the AE eCRF page, Action taken with study treatment = Drug withdrawn).
- **Adverse Events Leading to Death:** adverse event leading to death (as recorded on the AE eCRF page, Outcome = Fatal, as well as AEs of Grade 5).
- **Immune Related Adverse Events (irAEs):** immune related adverse events are identified via customized MedDRA PT queries and additionally classified by medical assessment according to case definition (two level approach). Details are included in [Appendix IV](#).
- **Infusion Related Reactions (IRRs):** IRRs are identified based on a list of MedDRA PTs. The detailed criteria of the timing relationship to infusion are specified in [Table 14](#) of Appendix IV.

Unless otherwise specified, AEs will be summarized by number and percentage of subjects with the AE in the category of interest as described above, by treatment group, primary System Organ Class (SOC) and Preferred Term (PT) and by decreasing frequency based on the avelumab treatment arm.

Each subject will be counted only once within each SOC or PT. If a subject experiences more than one AE within a SOC or PT for the same summary period, only the AE with the strongest relationship or the worst severity, as appropriate, will be included in the summaries of relationship and severity.

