Within one adverse event, changes in toxicity grade, seriousness, or outcome are recorded as separate AE entries in the eCRF with start and end dates corresponding to the dates of change. In such cases, the start date of one entry will equal the end date of a previous entry. In the case that records report an event with the same preferred term in immediately consecutive periods and the severity of the reported event does not worsen, the records will be considered as one event in the analysis. All events will be maintained as separate records in the database, in order to maintain the full detailed history of the events and preserve traceability. The start date of the initial record in the sequence is

---

taken as start date of the entire event. Duration of the AE and the TEAE flag will be adjusted accordingly in the analysis. In the case that a subsequent record indicates a worsening of an ongoing event, the subsequent, worse record will be treated as a separate adverse event. If the subsequent, worse record is outside of the on-treatment period, it will not appear on the summaries/listings of TEAEs.

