### **16.2.2 Serious Adverse Events**

*Analysis sets: Safety-Induction Analysis Set, Safety-Maintenance Analysis Set*

The frequency (number and percentage) of subjects with each of the following will be presented for treatment-emergent SAEs by treatment group:

- SAEs by SOC and PT
- Related SAEs by SOC and PT

A listing of SAEs will also be provided with the relevant information, including a flag for SAEs with onset outside of the on-treatment period.

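### SAP 16.1 merges consecutive AE records on grade alone, so an Induction AE that turns serious in Maintenance without a higher grade is missing from the Maintenance SAE tables

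*SAP*

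**What the plan says.** SAP 16.1 describes how the data arrive: "changes in toxicity grade, seriousness, or outcome are recorded as separate AE entries in the eCRF". Three kinds of change can therefore open a new record.

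For analysis, adjacent records with the same preferred term are joined if "the severity of the reported event does not worsen, the records will be considered as one event in the analysis". The first record supplies the start date, and "Duration of the AE and the TEAE flag will be adjusted accordingly in the analysis". When a later record is a worsening, "the subsequent, worse record will be treated as a separate adverse event".

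The same section defines TEAEs as "those events with onset dates occurring during the on-treatment period or if the worsening of an event is during the on-treatment period", with one on-treatment period for Induction and another for Maintenance. SAP 16.2.2 limits the SAE tables in the same way: frequencies "will be presented for treatment-emergent SAEs by treatment group".

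The protocol fixes what severity means. In section 7.4.1.1, on CTCAE, it states: "A general grading (severity/intensity; hereafter referred to as severity) scale is provided at the beginning of the above referenced document". Seriousness is defined separately in that section, by criteria such as hospitalisation. SAP 16.1.1 also uses severity to mean the NCI-CTCAE grade.

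**The concern.** Three attributes can open a record, but only one of them is checked before records are joined. A move from non-serious to serious with no rise in grade passes the test, so the two records become one event carrying the earlier date.

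Every randomised subject comes from 12 weeks of an oxaliplatin doublet, so AEs ongoing at the start of Maintenance are to be expected. If such an AE leads to hospitalisation on randomised treatment, the date that matters for the Maintenance comparison is the date it became serious. Under the rule as written, that date is replaced by an Induction date and the event leaves the Maintenance table. Safety and tolerability of avelumab is a stated secondary objective, and the by-arm SAE table is one of its main outputs.

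**Working it through.** The plan gives no figure to reproduce here, so the check is to follow the rule as written.

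**Inputs**

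- Join test (SAP 16.1): same preferred term, immediately consecutive records, grade not higher than in the preceding record.
- Date and flag (SAP 16.1): the joined event starts with its first record; a record with a higher grade starts a new event.
- Grade scale (Protocol 7.4.1.1): the top grade is "Grade 5 or Death".
- AE leading to death (SAP 16.1): fatal outcome on the eCRF, or Grade 5.
- Deaths table (SAP 16.2.1): taken from the death and survival follow-up forms, not from AE records.
- Phase (SAP 10): the Induction on-treatment period ends no later than the day before Maintenance treatment starts.

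**Rule applied to constructed record pairs.** In each pair the first record starts 10 days before the first Maintenance dose, and the second starts 20 days after it, on the day the first ends. These are illustrations, not trial data.

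| First record | Second record | Grade higher? | Result |
|---|---|---|---|
| Grade 3, non-serious | Grade 3, serious | No | Joined, dated to Induction, absent from Maintenance SAE table |
| Grade 3, non-serious | Grade 2, serious | No | Joined, dated to Induction, absent from Maintenance SAE table |
| Grade 2, non-serious | Grade 3, serious | Yes | Separate, counted as Maintenance SAE |
| Grade 3, non-serious | Grade 5, fatal | Yes | Separate, counted in Maintenance TEAEs leading to death |
| Grade 4, serious | Grade 5, fatal | Yes | Separate, counted in Maintenance TEAEs leading to death |
| Grade 4, serious | Grade 4, outcome fatal, not re-graded | No | Joined, dated to Induction, absent from Maintenance TEAEs leading to death |

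The test compares grades only, so the first row reads the same with Grade 1 or Grade 2 in both records.

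**Attributes of a joined event.** The SAP does not say which seriousness or outcome a joined event carries. If it takes the later, serious status, the event appears as an Induction SAE. If it keeps the first record's status, it appears in neither phase's SAE table. The Maintenance count is short by one either way.

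**Which AEs are exposed.** Protocol 7.4.1.1 already requires clinical Grade 4 and 5 AEs to be reported as serious. A change from non-serious to serious at constant grade is therefore mainly a matter of Grades 1 to 3 and of Grade 4 laboratory abnormalities.

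**Is joining across seriousness intended?** The SAP 4.1 change list for Version 2.0 describes the rule for section 16.1 as pooling entries of the same AE that differ in grade, outcome or seriousness. That supports the literal reading.

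**The case against.** **Worsening might include seriousness.** Neither the TEAE definition nor the sentence on worse records ties worsening expressly to grade. SAP 9 also says that data are not pooled across phases, and TEAEs are defined by phase. These passages make the text less settled, but they do not displace the explicit severity test. SAP 9 is a general statement, and the join rule has no phase limit. If two programmers could read the rule differently and obtain different SAE counts, the wording still needs repair.

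**The data stay visible.** Records remain separate in the database, and the AE listings include every AE. The SAE listing flags onset outside the on-treatment period, and SAP Table 8 tabulates Induction serious TEAEs for the Safety-Maintenance set. All of this is true, but a listing does not correct a by-arm incidence table. An event dated inside the Induction on-treatment period might also not be flagged.

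**Few AEs may carry over at Grade 2 or above.** Eligibility is checked again at Re-baseline, and exclusion criterion 13 bars persisting Grade 2 or higher toxicity from prior therapy, alopecia excepted. If Induction chemotherapy counts as prior therapy, which the text leaves open, some of the illustrated subjects should not be randomised. This reduces the exposed pool. It does not empty it, because Grade 1 events and events not attributed to therapy remain.

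**Safety is descriptive.** No test, alpha or primary endpoint is involved. That stands and limits the weight of the point.

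**Conclusion.** Followed as written, SAP 16.1 gives a wrong Maintenance SAE count for any AE that starts in Induction and becomes serious in Maintenance at the same or a lower grade. Each such event takes one SAE out of the by-arm Maintenance table. The number of events cannot be derived from the documents. The conclusion rests on severity meaning CTCAE grade, and on the join rule applying across the phase boundary because nothing restricts it.

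Three stronger readings are tempting and are not supported:

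- A reader might infer that AEs turning fatal also leave the Maintenance death tables. A correctly graded fatal AE is Grade 5, hence a worsening and a separate event. Only a record with a fatal outcome left below Grade 5 would be absorbed, and then only from the table of TEAEs leading to death. The SAP 16.2.1 deaths table does not use AE records and is unaffected.
- A reader might infer the opposite error as well, with an AE that turns serious after the on-treatment window being counted as an on-treatment SAE. That requires the joined event to inherit the later seriousness, which the SAP does not state.
- A reader might infer a bias between arms, since only the control arm continues the Induction drugs. The documents give nothing from which to establish its existence, direction or size.

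The point is worth correcting before database lock. It does not threaten the trial's main conclusions.

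**What to change.** In SAP 16.1, treat a change from non-serious to serious, or to a fatal outcome, as a worsening alongside a rise in grade. The later record then becomes a separate event with its own start date for the TEAE, SAE and fatal flags, as already happens for a grade increase. Add a sentence stating which seriousness and outcome a merged event carries.

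The cost is a short text change and one derivation change before database lock, with slightly higher event counts. SAP 16.1 counts each subject once per system organ class and preferred term, so splitting records within one phase does not count a subject twice in the incidence tables.

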### 16.1.1 All Adverse Events

*Analysis sets: Safety-Induction Analysis Set, Safety-Maintenance Analysis Set*

Adverse events will be summarized by worst severity per subject according to the National Cancer Institute – Common Terminology Criteria for Adverse Events (NCI-CTCAE version 4.03), using the latest version of MedDRA PT as event category and MedDRA primary SOC body term as Body System category.

In case a subject has events with missing and non-missing grades, the maximum of the non-missing grades will be displayed. No imputation of missing grades will be performed.

The following tables will be created:

- The overall summary table of AEs will include the following categories:
    - TEAEs
    - TEAEs, grade  $\geq 3$
    - Related TEAEs
    - Related TEAEs, grade  $\geq 3$
    - TEAEs leading to permanent treatment discontinuation
    - Related TEAEs leading to permanent treatment discontinuation
    - Serious TEAEs
    - Related serious TEAEs
    - TEAEs leading to death
    - Related TEAEs leading to death
    - Treatment-emergent irAEs
    - Treatment-emergent IRRs
    - Related treatment-emergent IRRs
  - TEAEs by SOC and PT and worst grade
  - Related TEAEs by SOC and PT and worst grade
  - TEAEs leading to death by SOC and PT
-

- Related TEAEs leading to death by SOC and PT
- TEAEs by SOC and PT: displaying in separate columns the All TEAEs / Related TEAEs / Grade  $\geq 3$  TEAEs / Related Grade  $\geq 3$  TEAEs
- TEAEs Excluding SAEs, with Frequency  $\geq 5\%$  in any treatment arm by SOC and PT

In addition, a listing of AEs with onset or worsening date after the on-treatment period will also be provided.

### 16.1.2 Adverse Events Leading to Treatment Discontinuation

*Analysis sets: Safety-Induction Analysis Set, Safety-Maintenance Analysis Set*

The frequency (number and percentage) of subjects with each of the following will be presented for TEAEs leading to permanent discontinuation by treatment group:

- TEAEs leading to treatment discontinuation by SOC and PT
- Related TEAEs leading to treatment discontinuation by SOC and PT

A listing of all TEAEs leading to treatment discontinuation will also be provided, including the relevant information.

## 16.2 Deaths, Other Serious Adverse Events, and Other Significant Adverse Events

### 16.2.1 Deaths

*Analysis sets: Safety-Induction Analysis Set, Safety-Maintenance Analysis Set*

All deaths, deaths within 30 days after last dose of randomized study treatment, deaths within 60 days after the date of first dose of randomized study treatment, and primary reason for death will be tabulated based on information from the “Death” and “Survival Follow-Up” CRFs.

- All Deaths
- Deaths within 30 days after last dose of study treatment
- Deaths within 60 days after first dose of study treatment
- Primary Reason for Death
  - Progressive disease and/or disease related condition
  - Adverse event related to study treatment
  - Adverse event not related to study treatment

- Other
- Unknown

In addition, date and primary reason for death will be provided in a data listing together with selected dosing information (study treatment received, date of first / last dose administration, dose and number of infusions received of randomized study treatment) and will include the following information:

- AEs with fatal outcome (list preferred terms of AEs with outcome = Fatal, as well as AEs of Grade 5)
- Flag for death within 30 days of last dose of randomized study treatment
- Flag for death within 60 days of first dose of randomized study treatment

### **16.2.2 Serious Adverse Events**

*Analysis sets: Safety-Induction Analysis Set, Safety-Maintenance Analysis Set*

The frequency (number and percentage) of subjects with each of the following will be presented for treatment-emergent SAEs by treatment group:

- SAEs by SOC and PT
- Related SAEs by SOC and PT

A listing of SAEs will also be provided with the relevant information, including a flag for SAEs with onset outside of the on-treatment period.

### **16.2.3 Other Significant Adverse Events**

*Analysis sets: Safety-Maintenance Analysis Set*

The following tables will be created for Maintenance Phase treatment-emergent irAEs by treatment group. Separate summary tables will present potential irAEs (those identified solely by MedDRA preferred term) and medically assessed irAEs (which meet the criteria outlined in [Appendix IV](#)). For the potential irAE tables, both treatment arms will be presented with counts, as applicable. Only the counts for the avelumab arm will be displayed in the medically assessed irAE summary tables. “Cluster” is a compilation of PTs that are categorized by immune-related event of special interest.

- The overall summary of irAEs table will include the following categories:
  - All irAEs
  - irAEs leading to death, by Cluster and PT
  - irAEs, by Cluster and PT

- irAEs, Grade  $\geq 3$ , by Cluster and PT
- irAEs leading to permanent treatment discontinuation, by Cluster and PT
- irAEs by Cluster and PT and worst grade
- irAEs leading to death, by Cluster and PT
- irAEs by Cluster and PT
- irAEs, grade  $\geq 3$ , by Cluster and PT
- irAEs leading to permanent treatment discontinuation by Cluster and PT
- irAEs by Cluster and PT and worst grade

A listing of all potential and reviewed irAEs will be provided with the relevant information and a flag for irAEs with onset outside of the on-treatment period.

The frequency (number and percentage) of subjects with each of the following will be presented for treatment emergent IRRs, by treatment group:

- The overall summary of IRR table will include the following categories:
    - All IRRs
    - Related IRRs
    - Serious IRRs
    - Related serious IRRs
    - IRRs, Grade  $\geq 3$
    - Related IRRs, Grade  $\geq 3$
    - IRRs leading to permanent treatment discontinuation
    - Related IRRs leading to permanent treatment discontinuation
    - IRRs leading to death
    - Related IRRs leading to death
  - IRRs leading to death, by PT
  - Related IRRs leading to death, by PT
  - IRRs, by PT
  - IRRs, Grade  $\geq 3$ , by PT
  - Related IRRs, by PT
  - Related IRRs, Grade  $\geq 3$ , by PT
  - IRRs leading to permanent treatment discontinuation, by PT
-

- Related IRRs leading to permanent treatment discontinuation, by PT
- Serious IRRs, by PT
- Related serious IRRs, by PT
- Time related to first onset of an IRR (infusion 1, infusion 2, infusion 3, infusion 4 or later)

A listing of all IRRs will also be provided with the relevant information.

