7.4.1.3 Definition of the Adverse Event Reporting Period

The AE reporting period for safety surveillance begins when the subject is initially included in the trial (date of first signature of informed consent) and continues for all SAEs and treatment-related non-serious AEs through the study's Safety Follow-up Phone Call, defined as 90 days (± 1 week) after the last IMP.

Any SAE assessed as related to the trial treatment must be reported whenever it occurs, irrespective of the time elapsed since the last administration.

7.4.1.4 Procedure for Reporting Serious Adverse Events, Adverse Events of Special Interest and Dose-Limiting Toxicities

In the event of any new SAE occurring during the reporting period, the Investigator must immediately (within a maximum 24 hours after becoming aware of the event) inform the Sponsor or its designee using the SAE Report Form following specific completion instructions.

In exceptional circumstances, an SAE (or follow-up information) may be reported by telephone; in these cases, a SAE Report Form must be provided immediately thereafter.

Relevant pages from the eCRF may be provided in parallel (for example, medical history, concomitant drugs). Additional documents may be provided by the Investigator, if available (for example, laboratory results, hospital report, autopsy report). In all cases, the information provided on the SAE Report Form must be consistent with the data about the event recorded in the eCRF.

The Investigator must respond to any request for follow-up information (for example, additional information, outcome, final evaluation, other records where needed) or to any question the

Sponsor/designee may have on the AE within the same timelines as those noted above for initial reports. This is necessary to ensure prompt assessment of the event by the Sponsor or designee and (as applicable) to allow the Sponsor to meet strict regulatory timelines associated with expedited safety reporting obligations.

Requests for follow-up will usually be made via the responsible monitor, although in exceptional circumstances the Global Drug Safety Department of the Sponsor may contact the Investigator directly to obtain clarification or to obtain further information or to discuss the event.

7.4.1.5 Safety Reporting to Health Authorities, Independent Ethics Committees/ Institutional Review Boards and Investigators

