**Definition of On-Treatment period:**

For the Induction Phase, the on-Treatment period is defined as the time from the first dose of induction chemotherapy treatment through the earliest of (the date of the last dose of Induction chemotherapy + 30 days, start day of new anti-cancer drug therapy – 1 day, date of Maintenance Phase study treatment start – 1 day).

For subjects randomized to the avelumab arm or the control arm and receive chemotherapy, the on-treatment period is defined as the time from the first dose of randomized treatment through the earliest of (last dose of study treatment + 30 days, start day of subsequent anti-cancer drug therapy – 1 day). For subjects randomized to the control arm and receive BSC-only, study treatment is considered to start on the day of the Week 1 Day 1 assessment visit and end on the earliest date given from among the following: date given on the Study Termination eCRF page and date of death. Thus, the on-treatment period for these subjects is defined as the time from the Week 1 Day 1 assessment visit to the earlier of (end of assessment date + 30 days, start of new anti-cancer drug therapy – 1 day).

The date of subsequent anti-cancer drug therapy is derived as outlined in Section 13.2.

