## Appendix IV Description of the Case Definition for Assessment of Immune-Related AEs and IRRs

### Immune-Related Adverse Events

Immune-related adverse events (irAEs) will be identified programmatically. AEs which satisfy all of the following criteria will be flagged as immune-related:

- 1) The AE preferred term matches a preferred term on the list of pre-selected MedDRA terms.
- 2) The AE onset occurs after the first study drug administration and no more than 90 days after last dose.
- 3) On the AE eCRF page, the question “Were Corticosteroids, Immunosuppressants, or hormonal therapy (e.g. Thyroid) applied?” has the answer “Yes” selected.
- 4) On the AE eCRF page, either:
  - a. The question “Does any of the following provide a clear etiology for the event?” has the answer “No” selected, indicating that the AE is not attributable to underlying cancer disease/PD, prior or concomitant medications/procedures, nor another medical condition such as an infection or pre-existing disease.

OR

- b. The AE eCRF indicates that a biopsy was performed and the question “Is the histopathology/biopsy consistent with an immune-mediated event?” has the answer “Yes” selected.

In the case that criteria (1) through (3) are met, and entries for condition (4) are missing, the following rules will be applied:

- If the answer to “Does any of the following provide a clear etiology for the event?” (4a) is missing, the event will be considered as irAE (irrespective of biopsy results).
- If the answer to “Is the histopathology/biopsy consistent with an immune-mediated event?” (4b) is missing, or if no biopsy was performed, and condition (4a) is not satisfied (i.e. “Yes” is selected as the answer to the question “Does any of the following provide a clear etiology for the event?”), the event will be considered as a non-irAE.

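### Cheap improvement: immune-related events starting after the on-treatment window meet the SAP's own definition but are listed rather than counted, and the medically assessed tables omit the control arm

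*SAP*

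**What the plan says.** The case definition is in SAP Appendix IV. Its timing criterion reads "The AE onset occurs after the first study drug administration and no more than 90 days after last dose". SAP 16.2.3 plans two sets of irAE tables: potential irAEs, identified by MedDRA preferred term alone, and "medically assessed irAEs (which meet the criteria outlined in" Appendix IV). Both sets fall under one lead-in: "The following tables will be created for Maintenance Phase treatment-emergent irAEs by treatment group".

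SAP 16.1 defines the term: "Treatment-emergent adverse events (TEAEs) are those events with onset dates occurring during the on-treatment period", or whose worsening falls in that period. For subjects on avelumab or chemotherapy, SAP 10 runs the on-treatment period "through the earliest of (last dose of study treatment + 30 days, start day of subsequent anti-cancer drug therapy" minus 1 day). SAP 16 limits all safety summary tables to this period. The overall adverse event table in SAP 16.1.1 has a line for treatment-emergent irAEs only. Protocol 8.5.5 likewise places irAEs among the treatment-emergent summaries.

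Collection runs longer than tabulation. Protocol 7.4.1.3 says reporting "continues for all SAEs and treatment-related non-serious AEs" up to the safety phone call 90 days after the last dose.

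On the arms shown, SAP 16.2.3 presents both in the potential-irAE tables, then says: "Only the counts for the avelumab arm will be displayed in the medically assessed irAE summary tables".

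**The concern.** Describing the safety and tolerability of avelumab is a stated objective (Protocol 4.2). Protocol 3.5 names irAEs as one of two primary identified risks, and Protocol 6.5.4 warns that they can take weeks to appear. The trial defines these events out to 90 days and collects the serious and treatment-related ones for that long. If the tables stop at 30 days or sooner, a reader of the clinical study report sees no count or percentage for late immune toxicity and must build one from listings.

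The single-arm display raises a second question. The Appendix IV criteria rest on preferred term, onset date, use of corticosteroids, immunosuppressants or hormones, and absence of another clear cause or a supportive biopsy. Events on chemotherapy can meet these too. Without control counts, the reader cannot judge how specific the definition is.

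**Working it through.** No sample-size, power or alpha figure is involved, and the plan states no figure to reproduce. The check compares the two windows, taking the day of last dose as day 0.

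**Inputs**
- Definition window: to day 90 (SAP Appendix IV).
- Table window: to the earlier of day 30 and the day before subsequent anti-cancer drug therapy (SAP 10, applied through SAP 16, 16.1, 16.1.1 and 16.2.3).
- Collection: all adverse events to the 30-day visit, then serious and treatment-related non-serious events to day 90 (Protocol 7.1.6 and 7.4.1.3).

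**New onsets**
- No subsequent drug therapy by day 30: 90 − 30 = 60 days are in the definition but outside the tables, and 60/90 = 67% of the post-dose days.
- Subsequent drug therapy starting on day d ≤ 30: the tables stop at day d − 1, so 90 − (d − 1) = 91 − d days are outside. For d = 15 this is 76 days.

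These are shares of post-dose time. They are not shares of events, and they leave out the treatment period itself, which both windows cover.

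**Worsening**
Under SAP 16.1, a record showing a worse grade becomes a separate event. If it falls outside the on-treatment period, it is left out of the treatment-emergent summaries. As an illustration, an irAE starting at Grade 2 on day 25 and reaching Grade 4 on day 35 is tabulated as Grade 2. The Grade ≥ 3, worst-grade and fatal irAE tables are all exposed to this, including for events already counted.

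**Where late events do appear**
- The irAE listing, with a flag for onset outside the window (SAP 16.2.3).
- The listing of adverse events starting or worsening after the on-treatment period (SAP 16.1.1).
- The serious adverse event listing, if serious (SAP 16.2.2).
- The table of all deaths by primary reason, if fatal (SAP 16.2.1), though not identified as an irAE.

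**Control arm and BSC-only subjects**
Appendix IV needs a first study-drug administration and a last dose. Control subjects on chemotherapy have both. BSC-only subjects have neither, yet SAP 9 puts them in the Safety-Maintenance set. Adding control counts therefore requires an anchor rule for them.

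**The case against.** A reader might infer that the SAP contradicts itself. The documents do not support that. Appendix IV decides whether an event is immune-related, and the treatment-emergent rule decides whether it enters a table. The second can sit inside the first. The flag in the irAE listing only makes sense if the definition is the wider of the two. The tables are labelled treatment-emergent, as Protocol 8.5.5 plans, and serious adverse events, also collected to day 90, are handled the same way. This part of the objection stands.

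A reader might also infer that late immune toxicity goes unreported, or that irAEs have no control rate. Neither follows. Late events are full records in the listings, and the potential-irAE tables show both arms. What remains is that late events are not counted and that the medically assessed tables show avelumab only.

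A third tempting reading is that the 90-day window should become the main display. After the 30-day visit only serious and treatment-related events are collected, and some follow new anti-cancer therapy. A single 90-day rate would mix two collection rules. That is a good reason to make it supplementary.

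Finally, the SAP contents list has a redacted entry between 16.2.3 and 16.3, so nothing can be said about irAE tables beyond the visible text.

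**Conclusion.** The point holds as a cheap improvement. In the visible SAP text, an irAE that meets Appendix IV but starts after the on-treatment period gets no count or percentage in any irAE table, and a later worsening does not raise the tabulated grade. At least 60 of the 90 post-dose days in the definition are affected, and more where subsequent drug therapy begins within 30 days. How many events this involves cannot be computed, so no size can be put on any understatement of the irAE rate.

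The single-arm display of medically assessed irAEs is a separate, smaller gap. Filling it assumes that the eCRF questions used in Appendix IV were also completed for control-arm events. The SAP describes them as part of the adverse event page and states no restriction to avelumab.

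No efficacy endpoint, error rate or data collection is touched.

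**What to change.** Keep the treatment-emergent irAE tables as the main display. In SAP 16.2.3:

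1. Add a supplementary table of medically assessed irAEs (any grade, Grade ≥ 3, worst grade, fatal) over the full Appendix IV window, regardless of subsequent therapy and using the worst grade reached in that window.
2. Show both arms in the medically assessed tables.
3. State the anchor for BSC-only subjects, for example the BSC-only treatment start (Week 1 Day 1 visit) and end date in SAP 10, or show these subjects separately. SAP 10 lists the components of that end date differently under its study-treatment and on-treatment definitions, so name the one used.
4. Footnote that on days 31–90 only serious and treatment-related non-serious events are collected, and that some events follow new anti-cancer therapy.

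The cost is a short SAP amendment and a few extra tables from data already collected. The drawback is that the 90-day figures need the footnote to be read correctly and are not directly comparable with the 30-day ones.
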